**NCT04702191**

**Statistical analysis plan: 3 April 2024**

## Introduction and trial design

Promoting Healthy Families is a three-arm trial undertaken in the province of Ontario, in which Triple P and Circle of Security Parenting Program (COSP) are compared against a treatment as usual (TAU) control in four community-based agencies. Randomisation was undertaken stratified by agency using a block size of 6. The trial included baseline, post-intervention, six-month and 12-month assessment points. Two further waves at three and nine months focused on service use.

This statistical analysis plan (SAP) is an addendum to the original protocol for the trial, and includes an updated account of measures used to capture psychosocial outcomes. Details of the statistical analysis plan largely mirror those in the original protocol, but in the event of any differences, the current SAP supersedes the protocol. Outcomes relating to health economic assessment (service use, quality of life), parenting observations and psychophysiological assessments are not included in the SAP and will be addressed in future addenda.

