Both the Marital Conflict Questionnaire and DAS-7 pertain only to people who reported being partnered at a given assessment point. We will assess any changes in eligibility for these measures over assessment points and use conditional imputation to account for these variables. In addition, because CTSPC-R was only administered to a subset of participants for whom home visits were possible, we will not include CTSPC-R in any imputation models.

**Effect estimation.** The general framework for effect estimation will be generalised linear mixed-effects models, with measurements (level 1) nested within families (level 2). The general form of each model is to include terms at level 1 for categorical time and for the interaction of intervention by categorical time, and at level 2 for study site as the stratification factor. This is equivalent to a model where the baseline measure is constrained to be equal between groups. Consistent with guidance from Coffman et al. (2016), we will not include a level 2 intervention term as this is essentially uninterpretable in the context of randomisation.

For each outcome model, we will select an appropriate outcome distribution, preferring an identity link where possible. If necessary to accommodate distributional violations, we will use percentile-based confidence intervals, undertaking cluster-level bootstrapping within each imputation and pooling runs to generate confidence intervals. In situations where variables have a limited range and discrete values, we will consider use of an ordered logit model. We will use Rubin's rules to combine estimates from multiple imputations.

The test of effectiveness will focus on the six-month value of the outcome. Correspondingly, we will examine the intervention-by-time interaction for the six-month assessment point for each intervention, and undertake a Wald test for each interaction (or, if bootstrapped models are used, examine a 97.5% confidence interval).

**Sensitivity analysis.** We will re-estimate all outcome models using unimputed data.

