### Additional analyses

**Effect modification analyses.** We will explore moderation of intervention effects at the six-month and 12-month assessment point for primary outcomes, child outcomes and the Brief Child Abuse Potential Inventory. To simplify analysis, we will not include post-intervention estimates in these models. Each candidate moderator will be interacted with time and with intervention by time, and a Wald test will be computed on the relevant three-way interaction terms to establish the presence of effect modification. Candidate moderators include study site (given differences in TAU across each site), baseline characteristics described above, and baseline values of child conduct problems (SDQ total problems scale) and of parental distress (CESD-10).

To evaluate the presence of moderation by baseline value of the outcome, we will consider two strategies. The first is to estimate random slope models and compare models with intercept-slope covariances (i.e. with unstructured covariance matrices of random effects) against those without using standard inferential tests. However, this may pose challenges for convergence and interpretation. In the event that it does, we will use time-by-time analyses with an appropriate ANCOVA model with terms for intervention allocation, stratum and baseline value of the outcome as predictors, in addition to candidate moderators. Each candidate moderator will be interacted with intervention status, and a Wald test will be computed on the interaction term to establish the presence of effect modification.

**Mediation analyses.** We will use a fully longitudinal mediation model to explore causal pathways to intervention impacts where a) a plausible relationship exists between the intervention, a mediator and an outcome; b) the effect estimate of the mediator is significant at six months; and c) the effect estimate of the outcome is significant at 12 months (using a  $p < 0.05$  threshold). This model will include paths between intervention allocation, mediator and outcome, and will control for site and for mediator and outcome values at baseline.

Indirect effects will be estimated via percentile-based confidence intervals derived from bootstrapping to account for asymmetries in the confidence interval induced by multiplying two regression terms. Separate indirect treatment effects will be reported for each intervention compared to TAU.

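### Site enters the longitudinal models only as a time-constant effect, so the six-month tests are slightly conservative; adding site-by-time is a minor, nearly free improvement

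*SAP*

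**What the plan says.** The Introduction and trial design section states that "Randomisation was undertaken stratified by agency using a block size of 6", and that the two programmes "are compared against a treatment as usual (TAU) control in four community-based agencies".

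Under Effect estimation (Analysis strategy section), every outcome model carries categorical time and its interaction with intervention among the repeated measurements, plus a term "at level 2 for study site as the stratification factor". No site-by-time term is listed. On baseline handling the SAP adds: "This is equivalent to a model where the baseline measure is constrained to be equal between groups". For the effectiveness test, "we will examine the intervention-by-time interaction for the six-month assessment point for each intervention", with a Wald test for each intervention. The Analysis principles section sets 0.025 for each comparison within a primary outcome.

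Site meets time only under Effect modification analyses (Additional analyses section): "Candidate moderators include study site (given differences in TAU across each site"). There each moderator is crossed with time and with intervention by time. That section also holds a contingent fallback, an "ANCOVA model with terms for intervention allocation, stratum and baseline value of the outcome as predictors".

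**The concern.** A level-2 site term fixes each agency's distance from the others at one value for baseline, post-treatment, six and 12 months. The decisive test, however, concerns the six-month value with baseline taken into account. If families at some agencies improve more than at others whatever their arm, that variation has no term of its own and at least part of it goes into the residual.

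Blocks within agency balance the arms at each agency, so a shift shared by all arms largely cancels from the arm contrast. The real sampling error excludes it while the model's reported error includes it. At stake are Wald tests that reject a little too rarely and confidence intervals that are a little too wide.

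**Working it through.** **Inputs from the SAP.** Four agencies, three arms, blocks of 6; the model terms and six-month test set out above; two-sided 0.05 split over two comparisons.

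**Assumptions, because the SAP gives no figures for them.** n = 80 or 160 families per arm; correlation ρ = 0.6; between-agency SD of change τ = 0 to 0.4 outcome SD; four equal agencies; no missing data; true effects of 0.42, 0.35 or 0.27 SD.

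**Step 1: the plan's own figure.** 0.05/2 = 0.025, which reproduces; the two-sided critical value is 2.2414. There is no stated sample size or power to reproduce.

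**Step 2: true sampling error.** With arms balanced within agency, a shared shift cancels. With baseline constrained equal, SE = √[(2/n)(1 − ρ²)].
- n = 80: √(0.025 × 0.64) = 0.1265
- n = 160: √(0.0125 × 0.64) = 0.0894

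Neither depends on τ.

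**Step 3: an unfavourable bound.** If all agency variation fell into the six-month residual, the SE ratio would be √[(1 − ρ² + τ²)/(1 − ρ²)].
- τ = 0.2: √(0.68/0.64) = 1.031
- τ = 0.4: √(0.80/0.64) = 1.118

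For a design with 80% power, 2.2414 + 0.8416 = 3.083.
- 3.083/1.031 − 2.2414 = 0.749, power 77.3%
- 3.083/1.118 − 2.2414 = 0.516, power 69.7%

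This is too pessimistic for two reasons. The site main effect is estimated from all four occasions and absorbs part of a shift. The bound also lets the estimate itself become more variable, which step 2 rules out.

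**Step 4: simulation of the models, shift shared by all arms.** A: unstructured covariance, effect 0.42 SD, 1,200 trials per setting. B: random family intercept, REML, effect 0.35 SD (n = 80) or 0.27 SD (n = 160), 1,500 trials per setting. C: a separate run with unstructured covariance.

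| Run | n per arm | τ | Model SE, site only | Model SE, site by time | Ratio | Power, site only vs site by time |
|---|---|---|---|---|---|---|
| A | 80 | 0.2 | 0.1275 | 0.1256 | 1.015 | 83.8% vs 84.8% |
| A | 80 | 0.3 | 0.1302 | 0.1261 | 1.033 | 82.5% vs 84.8% |
| A | 80 | 0.4 | 0.1330 | 0.1260 | 1.056 | 83.5% vs 86.6% |
| B | 80 | 0.2 | 0.1278 | 0.1265 | 1.010 | 69.1% vs 69.8% |
| B | 80 | 0.4 | 0.1315 | 0.1264 | 1.040 | 65.7% vs 69.2% |
| B | 160 | 0.2 | 0.0903 | 0.0894 | 1.010 | 78.5% vs 79.2% |
| B | 160 | 0.4 | 0.0930 | 0.0894 | 1.040 | 74.4% vs 76.2% |
| C | 80 | 0.2 | 0.1273 | 0.1258 | 1.012 | not run |
| C | 80 | 0.4 | 0.1311 | 0.1258 | 1.042 | not run |

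With site by time, the model SE agrees with step 2. Each power figure carries about 1 point of Monte Carlo error.

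**Step 5: bias and type I error (run B, τ = 0.4).** At n = 80 and a true effect of 0.35, the mean estimate is 0.349 under both models and the empirical SE 0.1284 under both. The Monte Carlo error of that SE is about 0.1284/√3000 = 0.0023, so it is compatible with 0.1265. Type I error at nominal 0.025 is 0.021 (site only) vs 0.026 (site by time) at n = 80, and 0.016 vs 0.023 at n = 160, each with Monte Carlo error of about 0.004. Arithmetic points the same way: 2.2414 × 0.1315/0.1265 = 2.330, a two-sided level of about 0.020.

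**Step 6: shift in the TAU arm only, τ = 0.4.** Model SE, site only vs site by time:
- A: 0.1306 vs 0.1297 (0.7%)
- B, n = 80: 0.1285 vs 0.1279 (0.5%), power 69.9% vs 70.2%
- B, n = 160: 0.0909 vs 0.0904 (0.6%), power 76.0% vs 76.1%

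**Step 7: no shift.** In run B the two model SEs are equal: 0.1264 at n = 80 and 0.0894 at n = 160. Run C also found no cost, including with unequal agencies.

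**The case against.** The strongest reply is that nothing here is wrong. The SAP adjusts for its stratification factor, a main effect is common practice, and any finding of effectiveness stays valid. All of that stands, and it is why the point is one of efficiency only.

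Three stronger readings are tempting, and the document does not support them.

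- A reader might infer from the SAP's remark on TAU that a material loss is documented. It is not. Agencies that differ in TAU produce a difference by site, arm and time, of which site by time picks up only the part shared across arms; step 6 puts that below 1% of the SE. The 1% to 5% figures need agency shifts common to all arms, which the SAP neither reports nor rules out. The term suited to TAU differences is the three-way one already planned as moderation.
- A reader might infer that the precision gained by stratifying is thrown away. The estimate and its actual variability are practically the same under both models; only the reported error is somewhat large.
- A reader might see a contradiction between the longitudinal model and the ANCOVA fallback. The fallback is exploratory and uses one follow-up time, so a stratum main effect is the only stratum adjustment it needs. The two models differ in form and do not conflict.

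It is also fair to say that the size rests wholly on assumed values, and that adding the term was not shown to be harmless in ordered-logit or partnered-only models. The fix is limited accordingly.

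**Conclusion.** The point holds as a minor one. Site enters the longitudinal models only as a constant shift, so agency differences in change that all arms share are partly counted as error in the six-month tests and intervals. The direction is conservative. A reader might take this as a sign of bias, inflated type I error or an invalid primary analysis; the checks show none of these.

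With 80 families per arm, correlation 0.6 and shared shifts of 0.2 SD, the model SE is 1.0% to 1.5% too large. At 0.4 SD it is 4.0% to 5.6% too large, depending on the covariance structure. Power falls by about 1 to 3 points (0.7 to 3.5 across the runs). With differences in TAU alone the effect on the SE stays under 1%, and with no site-by-time variation nothing is lost. The true size cannot be fixed from the SAP.

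**What to change.** In the two primary-outcome models, and in the other longitudinal models with an identity link, replace the site main effect with site by categorical time, and keep intervention by time at zero at baseline. For ordered-logit outcomes and those asked only of partnered parents, allow the site main effect to stay if site-by-time cells are sparse. Leave the planned moderation analysis by site as it is, since it remains the analysis for differences in TAU.

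The cost is one line of SAP wording and nine fixed-effect parameters (3 site contrasts × 3 follow-ups), with no new data. The change belongs in the SAP before outcomes are compared by arm; if that has already happened, the version with site by time should be reported as a sensitivity analysis. If the main effect is kept by choice, one sentence giving the reason would settle the point.

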### Additional analyses

**Effect modification analyses.** We will explore moderation of intervention effects at the six-month and 12-month assessment point for primary outcomes, child outcomes and the Brief Child Abuse Potential Inventory. To simplify analysis, we will not include post-intervention estimates in these models. Each candidate moderator will be interacted with time and with intervention by time, and a Wald test will be computed on the relevant three-way interaction terms to establish the presence of effect modification. Candidate moderators include study site (given differences in TAU across each site), baseline characteristics described above, and baseline values of child conduct problems (SDQ total problems scale) and of parental distress (CESD-10).

To evaluate the presence of moderation by baseline value of the outcome, we will consider two strategies. The first is to estimate random slope models and compare models with intercept-slope covariances (i.e. with unstructured covariance matrices of random effects) against those without using standard inferential tests. However, this may pose challenges for convergence and interpretation. In the event that it does, we will use time-by-time analyses with an appropriate ANCOVA model with terms for intervention allocation, stratum and baseline value of the outcome as predictors, in addition to candidate moderators. Each candidate moderator will be interacted with intervention status, and a Wald test will be computed on the interaction term to establish the presence of effect modification.

**Mediation analyses.** We will use a fully longitudinal mediation model to explore causal pathways to intervention impacts where a) a plausible relationship exists between the intervention, a mediator and an outcome; b) the effect estimate of the mediator is significant at six months; and c) the effect estimate of the outcome is significant at 12 months (using a  $p < 0.05$  threshold). This model will include paths between intervention allocation, mediator and outcome, and will control for site and for mediator and outcome values at baseline.

Indirect effects will be estimated via percentile-based confidence intervals derived from bootstrapping to account for asymmetries in the confidence interval induced by multiplying two regression terms. Separate indirect treatment effects will be reported for each intervention compared to TAU.

***Exploratory analyses.*** We will undertake three sets of exploratory analyses: Triple P vs COSP, analyses for the CTSPC-R, and trajectory-based analyses.

***Triple P vs COSP.*** For all outcome models, we will re estimate analyses with COSP as the reference category to estimate

***CTSPC-R.*** Because of COVID-19 restrictions, collection of CTSPC-R data via home visit was severely restricted. Thus, we will analyse this as an exploratory outcome. The CTSPC-R is only collected at the 12-month assessment point. For this outcome, we will estimate a single-level model with terms for intervention arm and study site, using an appropriate outcome distribution and link function.

***Trajectory-based models.*** Given the multiple assessment points in this trial, we will also explore developing trajectory-based estimates of intervention impacts for primary outcomes and child outcomes. After considering the most likely functional form of the time relationship suggested in primary outcome models, we will treat time as continuous and describe the impacts of interventions on outcome trajectories using interaction terms for intervention status by linear or quadratic time trends.

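### The first-choice test of moderation by the baseline outcome tests an intercept-slope covariance, not a difference between arms

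*SAP*

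**What the plan says.** The section on effect modification states its aim as follows: "We will explore moderation of intervention effects at the six-month and 12-month assessment point for primary outcomes, child outcomes", and it adds the Brief Child Abuse Potential Inventory. Most moderators are tested by a three-way interaction of moderator, intervention and time.

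The baseline value of the outcome is handled separately: "To evaluate the presence of moderation by baseline value of the outcome, we will consider two strategies".

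- **First strategy.** Estimate random slope models and "compare models with intercept-slope covariances (i.e. with unstructured covariance matrices of random effects) against those without using standard inferential tests". The SAP does not say which variable carries the random slope, and it names no arm-specific covariance.
- **Second strategy.** The SAP cautions: "However, this may pose challenges for convergence and interpretation". If such problems arise, it moves to an ANCOVA at each time point with "terms for intervention allocation, stratum and baseline value of the outcome as predictors, in addition to candidate moderators". It continues: "Each candidate moderator will be interacted with intervention status, and a Wald test will be computed on the interaction term".

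The baseline scores listed as candidate moderators are SDQ total and CESD-10. The other candidates are site and family characteristics.

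**The concern.** Moderation by baseline means that the difference between an intervention and TAU changes with the starting level. An intercept-slope covariance describes how change relates to starting level within families. If that relation is the same in Triple P, COSP and TAU, there is no moderation, yet the covariance is not zero and the comparison can reject.

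The comparison also sits badly with Analysis principles, which makes Triple P vs TAU and COSP vs TAU the primary comparisons in every analysis. With a random time slope, the result is one answer pooled over arms, attached to neither intervention and to neither the six-month nor the 12-month point.

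At stake is a statement that benefit depends on initial severity, which bears on who is offered these programmes. It could rest on a pattern equally present in TAU, and a genuine dependence could go unseen.

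**Working it through.** **1. What the comparison tests.** For a family in arm *a*, let the latent starting level be u0 with variance s², and the latent slope be u1 = (b + g_a)·u0 + noise, with g = 0 in TAU. No moderation means g = 0 in both active arms. The within-arm covariance is (b + g_a)·s². With equal arms (assumed), the pooled covariance is s²·[b + (g_TripleP + g_COSP)/3].

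- *Random time slope:* the test asks whether the pooled covariance is zero. It can reject when g = 0 and b ≠ 0. It has almost nothing to detect when b = -(g_TripleP + g_COSP)/3.
- *Random slope on intervention-by-time only:* TAU has no slope, so a shared b in the active arms is credited to the intervention.
- *Both slopes:* the model without covariances also drops the shared one, so b is still among the parameters tested.

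**2. Inputs.** The SAP gives the waves in these models (baseline, 6 and 12 months, with post-intervention left out), three arms and a two-sided 5% level. Everything else is assumed: intercept SD 0.8, slope SD 0.25 per 6 months, residual SD 0.6, identity link, linear slope, no site effects, 500 runs per cell. The Monte Carlo standard error is about 1 point near 5% and 2 points near 50%. The SAP has no figure of its own to reproduce.

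**3. No moderation: percentage of runs rejecting, by latent intercept-slope correlation shared by all arms.**

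| Test | 0 | -0.1 | -0.2 | -0.3 | -0.5 | +0.3 |
|---|---|---|---|---|---|---|
| Random time slope, 100 per arm | 4 | 11 | 23 | 45 | 86 | 43 |
| Random time slope, 50 per arm | 4 | 7 | 17 | 27 | 61 | 25 |
| Intervention-by-time slope only, 100 per arm | 3 | 4 | 9 | 21 | 59 | 33 |

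The ANCOVA baseline-by-arm test stays at 3-6% throughout. A mixed model that keeps the intercept/time-slope covariance in both models, and tests only the added intervention part, stays at 3-7%. With both slopes random (300 runs, 100 per arm), rejection is 3% at correlation 0 and 25% at -0.3.

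Regression to the mean from residual error is not the cause. At correlation 0, observed change regresses on observed baseline with slope -0.6²/(0.8² + 0.6²) = -0.36/1.00 = -0.36, yet the covariance test rejects in 4%.

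**4. Moderation present but masked.** Take a shared correlation of +0.3, so b = 0.3 × 0.25/0.8 = 0.094, and let the effect of both interventions change by -0.14 per 6 months per unit of latent baseline. The pooled coefficient is 0.094 - (2 × 0.14)/3 = 0.094 - 0.093, or about 0. With 100 / 200 per arm, the random time slope comparison rejects in 4 / 6%, the 12-month ANCOVA interaction in 29 / 52%, and the corrected mixed model in 36 / 64%.

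**5. Different assumptions.** Intercept SD 1, residual slope SD 0.5 per 12 months, error SD 0.6, 200 runs per cell. Percentage rejecting at 50 / 100 / 150 per arm, or at 50 / 100 or 100 only where shown:

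| Truth | Time slope | Intervention-by-time slope only | Arm-specific vs common covariance | 6-month ANCOVA |
|---|---|---|---|---|
| No covariance, no moderation | 5 / 4.5 / 6.5 | 5 / 4 / 4 | 7 / 4.5 / 3 | 6 / 5 / 4 |
| b = -0.4 in all arms, no moderation | 93.5 / 100 / 100 | 67 / 87 / 99.5 | 3.5 / 6.5 / 5.5 | 3 / 5 / 4 |
| Moderation -0.4 in both, TAU b = +0.267 (50 / 100) | 7.5 / 5.5 | 19.5 / 36 | 46.5 / 76 | 18 / 31 |
| Moderation +0.4 and -0.4 (50 / 100) | 4 / 7 | 87.5 / 100 | 86.5 / 100 | 38 / 75 |
| Moderation -0.4 in both, TAU b = 0 (100) | 92.5 | 98 | 81.5 | 36 |

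The second row is a strong case: its latent correlation is -0.4/√(0.4² + 0.5²) = -0.62. False declarations occur under both placements of the slope. The near-complete failure to detect moderation belongs to the time-slope reading.

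**6. The fallback.** The analysis covers SDQ total, Overreactivity, SDQ Prosocial, the Brief Child Abuse Potential Inventory and CTSPC-R. The last has no baseline value: "The CTSPC-R is only collected at the 12-month assessment point". Among the other four, only SDQ total is both an outcome and a listed baseline moderator. For the remaining three, the ANCOVA text enters the baseline outcome as a predictor, separate from the moderators that are interacted with intervention.

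**The case against.** Five points can be made for the plan.

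- **The random slope is not named.** A slope on intervention-by-time uses some arm information, and a model with both slopes that tested only the intervention part would be sound. This is true, but the SAP describes unstructured against no covariance, and each of the three placements simulated was inflated by a shared covariance.
- **Time is categorical in the main model.** With three waves, a random intercept, two random time slopes (unstructured) and a residual variance need 7 parameters for 6 variance-covariance moments, so the model is not identified and the plan would move to ANCOVA. This is right for that reading. It leads to a fallback that still lacks the written interaction, and the linear-slope reading remains open.
- **The SAP itself warns about interpretation.** It does, but a model that converges cleanly can still answer the wrong question, and nothing in the text tells the analyst that this is the interpretation problem meant.
- **The fallback's purpose implies a baseline-by-arm term.** That is a fair inference from the paragraph's opening. For three outcomes it remains only an inference.
- **The figures are conditional.** They are. The test is near nominal at zero correlation, and it detects moderation well when TAU has no covariance and both interventions moderate in the same direction (92.5% at 100 per arm).

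**Conclusion.** The concern holds. As worded, the first strategy does not test whether the intervention effect differs by baseline level. It can declare moderation when change depends on starting level equally in all arms: 45% of runs for a time slope and 21% for an intervention-by-time slope, at an assumed correlation of -0.3 with 100 per arm. Under the time-slope reading it can also miss moderation almost completely (4-6%, against 29-52% for the 12-month ANCOVA interaction).

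The exact rates rest on assumed variances, correlations and arm sizes, on a linear slope and on an identity link. The direction follows from the algebra. The damage is limited to one exploratory analysis. The six-month effectiveness test, its Bonferroni control and the three-way interactions for the other moderators are unaffected. It should be corrected because following the stated order of methods can lead to a wrong conclusion.

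**What to change.** Replace the first strategy with one of these, named in advance.

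1. **ANCOVA as the main test.** At 6 and at 12 months, for SDQ total, Overreactivity, SDQ Prosocial and the Brief Child Abuse Potential Inventory, fit arm, stratum, baseline outcome and a written-out baseline-by-arm interaction. Give a Wald test for Triple P vs TAU and another for COSP vs TAU.
2. **Mixed model, if kept.** State which slopes are random, keep the intercept/time-slope covariance in both models, and test only the added intercept/intervention-slope covariance. Do this separately for each intervention, since opposite effects could cancel in a pooled test. The 3-7% and 36 / 64% figures above come from a version that pooled the two. This option had somewhat more power than ANCOVA in the masked case, but it is harder to fit.

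The section should also say that CTSPC-R is excluded here because it has no baseline. The cost is SAP wording only. No new data are needed, and imputation is already planned separately by arm, which suits a baseline-by-arm term.
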